### 6.3.3 Pomalidomide Dose Adjustments and Delays

Pomalidomide dose levels are outlined in Table 6-2, and dose adjustments for hematologic and nonhematologic toxicities are outlined in Table 6-3.

**Table 6-2 Pomalidomide Dose Levels**

Dose Level	Dose (mg)
Starting Dose	4 mg
-1	3 mg
-2	2 mg
-3	1 mg

Table 6-3: Dose Modifications Guidelines for Pomalidomide:		
NCI CTC Toxicity Grade	Onset Day 2-14 of Cycle	Onset <math>\geq</math> Day 15 of Cycle
Grade 3 neutropenia associated with fever (temperature <math>\geq 38.5^{\circ}\text{C}</math>) or Grade 4 neutropenia	
 
• Hold (interrupt) pomalidomide.
 
• Follow CBC weekly.
 
• If neutropenia has resolved to <math>\leq</math> grade 2 prior to Day 21, restart at next lower dose level and continue through Day 21. If neutropenia is the only toxicity for which a dose reduction is required G-CSF may be used and the dose maintained
 
	
 
• Omit pomalidomide for remainder of cycle
 
• See Instructions for Initiation of a New Cycle (6.3.1) and reduce the dose by 1 dose level. If neutropenia is the only toxicity for which a dose reduction is required. G-CSF may be used and the dose maintained for the next cycle at the investigators discretion.
 

Thrombocytopenia <math>\geq</math> Grade 3 (platelet count <math>< 50,000/\text{mm}^3</math>)	
 
• Hold (interrupt) pomalidomide.
 
• Follow CBC weekly.
 
• If resolves to <math>\leq</math> grade 2 prior to Day 21, restart at next lower dose level and continue through Day 21.
 
	
 
• Omit pomalidomide for remainder of cycle
 
• See Instructions for Initiation of a New Cycle (6.3.1) and reduce the dose by 1 dose level.
 

Non-blistering rash Grade 3  Grade 4	
 
• If Grade 3, hold (interrupt) pomalidomide. Follow weekly.
 
• If the toxicity resolves to <math>\leq</math> grade 1 prior to Day 21, restart at next lower dose level and continue the cycle through Day 21.
 
• Discontinue and remove from study.
 
	
 
• Omit pomalidomide for remainder of cycle.
 
• See Instructions for Initiation of a New Cycle (6.3.1) and reduce the dose by 1 dose level.
 
• Discontinue pomalidomide. Remove patient from study.
 

Desquamating (blistering) rash- any Grade	
 
• Discontinue pomalidomide. Remove patient from study.
 
	
 
• Discontinue pomalidomide. Remove patient from study.
 

Neuropathy Grade 3	
 
• Hold (interrupt) Pom. Follow at least weekly.
 
• If the toxicity resolves to <math>\leq</math> grade 1 (or to baseline at study entry) prior to Day 21, restart at next lower dose
 
	
 
• Omit pomalidomide for the remainder of the cycle.
 
• See Instructions for Initiation of a New Cycle (6.3.1) and reduce the dose by 1 dose level.
 

Table 6-3: Dose Modifications Guidelines for Pomalidomide:		
NCI CTC Toxicity Grade	Onset Day 2-14 of Cycle	Onset <math>\geq</math> Day 15 of Cycle
Grade 4	level and continue the cycle through Day 21. 
 
Discontinue pomalidomide. Remove patient from study.
 
	
 
Discontinue pomalidomide. Remove patient from study.
 

Venous thrombosis/embolism <math>\geq</math> Grade 3	
 
Hold (interrupt) pomalidomide and start anticoagulation; restart at investigator's discretion (maintain dose level).
 
	
 
Omit pomalidomide for remainder of cycle and start anticoagulation .
 

Hyperthyroidism or hypothyroidism	
 
Omit pomalidomide for remainder of cycle, evaluate etiology, and initiate appropriate therapy.
 
See Initiation of a New Cycle (6.3.1) and reduce dose by 1 dose level.
 
	
 
Omit pomalidomide for remainder of cycle, evaluate etiology, and initiate appropriate therapy.
 
See Initiation of a New Cycle (6.3.1) and reduce dose by 1 dose level.
 

other non-hematologic toxicity (non cardiac) <math>\geq</math> Grade 3	
 
Hold (interrupt) pomalidomide. Follow at least weekly.
 
If resolves to <math>\leq</math> grade 2 prior to Day 21, restart at next lower dose level and continue through Day 21.
 
	
 
Omit pomalidomide for remainder of cycle.
 
See Instructions for Initiation of a New Cycle (6.3.1) and reduce the dose by 1 dose level.
 

Grade 3 dyspnea, cardiac edema, arrhythmias OR any increase in NYHA class or NTproBNP <math>\geq</math> 30%  Grade 4	
 
Hold Pom. Follow biweekly. If resolves to baseline prior to Day 21, restart at next lower dose and continue through Day 21. If does not resolve to baseline by day 21, hold Pom for remainder of cycle. CC-4047 at next lower dose level and continue through Day 21.
 
Discontinue pomalidomide.
 
	
 
Omit pomalidomide for remainder of cycle.
 
See Instructions for Initiation of a New Cycle (6.3.1) and reduce the dose by 1 dose level.
 
Discontinue pomalidomide.
 

#### Dosage Adjustment for Strong CYP1A2 Inhibitors

Avoid concomitant use of pomalidomide with strong inhibitors of CYP1A2. Alternative treatments must be used.

#### Dosage Adjustment for Patients with Hepatic Impairment

For patients with mild or moderate hepatic impairment (Child-Pugh classes A or B), the recommended starting dose is 3 mg daily (25% dose reduction). For patients with severe hepatic impairment (Child-Pugh class C), the recommended dose is 2 mg (50% dose reduction)

Permanently discontinue pomalidomide for angioedema, skin exfoliation, bullae, or any other severe dermatologic reaction.

For other Grade 3 or 4 toxicities, hold treatment and restart treatment at 1 mg less than previous dose when toxicity has resolved to  $\leq$  to Grade 2 at the physician's discretion.

If pomalidomide is discontinued for toxicity, the patient may continue on study receiving daratumumab per study schedule with dexamethasone alone without pomalidomide.

Once pomalidomide is reduced for any toxicity, the dose may not be re-escalated.

#### 6.3.4 Clarithromycin Dose adjustments

Clarithromycin will be dose reduced by 50% to 250mg PO bid for CrCl  $<30$  mL/min during treatment as there is 20-40% renal excretion.

#### 6.3.5 Dexamethasone Dose adjustments

Dexamethasone dose levels are outlined in Table 6-4, and dose adjustments for adverse events are outlined in Table 6-5.

**Table 6-4 Dexamethasone Dose Levels**

Dose Level	Dose (mg)
Starting Dose (weekly)	40 mg
-1	20 mg
-2	12 mg
-3	8 mg

**NOTE:** The 20 mg dose of dexamethasone premedication must still be given before the injection on the day of each daratumumab administration regardless of any dexamethasone dose reductions. Therefore, the -2 and -3 dose level weekly dexamethasone dose adjustments only apply to dexamethasone doses on non-daratumumab administration weeks.

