#### *6.2.1.2 Concomitant Medications*

##### Pre-injection Medications

Administer the following premedications to reduce the risk of reactions to all patients 1-3 hours prior to every SC injection of daratumumab.

- Dexamethasone 20 mg IV or PO. Dexamethasone must be given intravenously prior to the first daratumumab dosing and oral administration may be administered prior to subsequent injections.
- Antipyretic (oral acetaminophen 650 mg to 1000 mg)
- Antihistamine (oral or intravenous diphenhydramine 25-50 mg IV)
- Leukotriene receptor antagonist (oral montelukast 10 mg)
- If FEV1  $\leq$  80% at baseline, strongly consider administering  $\beta$ 2-adrenergic agonist inhaler (e.g. albuterol)

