#### 6.2.4 Dexamethasone Administration

For Cycle 1, 20mg IV dexamethasone will be administered as a premedication on days 1 and 8 and 20 mg PO will be administered on days 2 and 9 (40mg weekly)\*\*; 40mg PO will be administered as premedication on days 15 and 22.

For Cycles 2-6, 40 mg PO dexamethasone will be administered weekly.

For Cycles 7-8, 20mg PO dexamethasone will be administered weekly.

For Cycle 9+, 20mg PO dexamethasone will be administered weekly.

When dexamethasone is administered on daratumumab treatment days, dexamethasone should be administered as a premedication prior to daratumumab injection.

\*\*Dexamethasone dosing if  $\geq 70$  years old- decrease dex dose by 50% in induction:

10 mg IV as premed on days 1 and 8 and 20mg PO on days 15 and 22 (Cycle 1)

10 mg PO the day after daratumumab on days 2 and 9 for Cycle 1 (total 20 mg/week)

20 mg PO as premedication weekly for cycle 2

20 mg PO weekly (cycles 3-6); 10 mg PO weekly (cycles 7+)

When taken orally, dexamethasone should be taken with food or milk to avoid gastrointestinal side effects. Missed doses can be taken as soon as the patient remembers if the next scheduled dose is 72 hours or more away. A double dose should not be taken to make up for a missed dose. If the patient vomits after taking a dose, the patient should not repeat the dose but should resume dosing at the time of the next scheduled dose.

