**Table 6-5 Dexamethasone Dose Adjustments for Adverse Events**

Adverse Event	Recommended Action
Dyspepsia, gastric or duodenal ulcer, gastritis Grade 1–2 (requiring medical management)	Treat with H2 blockers, sucralfate, or pantoprazole. If symptoms persist despite above measures, decrease dexamethasone dose by 1 dose level.
> Grade 3 (requiring hospitalization or surgery)	Hold dexamethasone until symptoms controlled. Restart at 1 dose decrement along with concurrent therapy with pantoprazole. If symptoms persist despite above measures, discontinue dex permanently.
Acute pancreatitis	Discontinue dexamethasone permanently.
Edema > Grade 3 (limiting function and unresponsive to therapy or anasarca)	Diuretics as needed, and restart dexamethasone at 1 dose decrement; if edema persists despite above measures, decrease dose another level. Discontinue dexamethasone permanently if symptoms persist despite second reduction.
Confusion or mood alteration > Grade 2 (interfering with function +/- interfering with activities of daily living)	Hold dexamethasone until symptoms resolve. Restart dexamethasone at 1 dose decrement. If symptoms persist despite above measures, reduce by another dose decrement.
Muscle weakness > Grade 2 (symptomatic and interfering with function +/- interfering with activities of daily living)	Decrease dexamethasone by 1 dose level. If weakness persists, decrease dose by 1 more dose level. Discontinue dexamethasone permanently if symptoms persist.
Hyperglycemia $\geq$ Grade 3	Treatment with insulin or other hypoglycemic agents as needed. If uncontrolled despite above measures, decrease dose by 1 dose level until levels are satisfactory.
Other nonhematologic Toxicity $\geq$ Grade 3 felt related to dexamethasone	Hold dexamethasone dose. Resume at 1 dose decrement when toxicity has resolved to Grade 2 or less or to baseline. If toxicity recurs, discontinue dexamethasone permanently.

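### The dexamethasone reduction ladder does not say what a dose level is counted from for patients scheduled at 20 or 10 mg, and the fixed 20 mg premedication contradicts the schedule at age 70 or over

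*Combined protocol and SAP*

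**What the plan says.** Table 6-4 is the only dexamethasone ladder in the protocol. The row "Starting Dose (weekly" is 40 mg; levels -1, -2 and -3 are 20, 12 and 8 mg. A note under the table adds two conditions. First, "The 20 mg dose of dexamethasone premedication must still be given before the injection on the day of each daratumumab administration", whatever reductions have been made. Second, "the -2 and -3 dose level weekly dexamethasone dose adjustments only apply to dexamethasone doses on non-daratumumab administration weeks".

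Table 6-5 expresses its reductions in levels or decrements, for example "decrease dexamethasone dose by 1 dose level", and gives no milligram value and no reference dose. Some rows end in stopping. Acute pancreatitis means permanent discontinuation, and the edema row says "Discontinue dexamethasone permanently if symptoms persist despite second reduction".

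Sections 4.1 and 6.2.4 schedule more than one weekly dose. Patients under 70 take 40 mg per week through cycle 6, and then "For Cycles 7-8, 20mg PO dexamethasone will be administered weekly", with 20 mg continuing from cycle 9. Patients aged 70 or over take 20 mg per week in cycles 1 and 2. After that the age rule reads "20 mg PO weekly (cycles 3-6); 10 mg PO weekly (cycles 7" and onward). In cycle 1 their premedication on days 1 and 8 is 10 mg IV, with 10 mg by mouth the next day.

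Section 6.2.1.2 lists dexamethasone 20 mg among the pre-injection drugs: "Administer the following premedications to reduce the risk of reactions to all patients 1-3 hours prior to every SC injection of daratumumab". It makes no exception for age or for a patient told to stop dexamethasone.

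**The concern.** The ladder fits a patient scheduled at 40 mg. It does not clearly fit anyone scheduled at 20 mg, and 10 mg is not on it. A site that must take a patient down one level has to guess whether to count from the 40 mg row or from the current dose, and the two counts give different results. The 20 mg premedication rule adds a second conflict that does not depend on that choice.

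The affected group may not be small. Section 1.1 puts the median age in myeloma at 69. It also says that clarithromycin slows the clearance of dexamethasone and raises corticosteroid exposure, so steroid toxicity is foreseeable. Sites could manage the same event differently. In rows that count reductions before permanent discontinuation, an empty step could be counted as a real one.

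**Working it through.** **Inputs.** Ladder: 40, 20, 12, 8 mg (Table 6-4). Premedication: 20 mg on each daratumumab day (Table 6-4 note; Section 6.2.1.2). Daratumumab weeks per 28-day cycle: 4 in cycles 1-2, 2 in cycles 3-6, 1 from cycle 7 (Section 4.1). Scheduled dexamethasone: Section 6.2.4.

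**The protocol's own figures reproduce.** Cycle 1 weekly totals are 20 + 20 = 40 mg under 70 and 10 + 10 = 20 mg at 70 or over. The 50% age rule gives 0.5 × 40 = 20 mg and 0.5 × 20 = 10 mg.

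**First step, weekly dose in a non-daratumumab week, two ways of counting.**

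| Scheduled dose | Level -1 as the fixed 20 mg rung | Next rung below the current dose |
|---|---|---|
| 40 mg | 20 mg (-50%) | 20 mg (-50%) |
| 20 mg | 20 mg (0%) | 12 mg (-40%) |
| 10 mg | 20 mg (+100%) | 8 mg (-20%) |

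The two counts agree only for patients scheduled at 40 mg. In cycles 1-2 every week is a daratumumab week, so the premedication rule below governs there.

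**28-day totals when counting from the current dose, with the premedication rule applied.** With n daratumumab weeks and next rung r, the total after one step is n × max(20, r) + (4 - n) × r.

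- Under 70, cycle 7 onward (n = 1, r = 12): 20 + 3 × 12 = 56 mg, against 4 × 20 = 80 mg scheduled (-30%).
- Age 70 or over, cycles 1-2 (n = 4, r = 12): 4 × 20 = 80 mg, against 80 mg scheduled (0%).
- Age 70 or over, cycles 3-6 (n = 2, r = 12): 2 × 20 + 2 × 12 = 64 mg, against 80 mg scheduled (-20%).
- Age 70 or over, cycle 7 onward at 10 mg (n = 1, r = 8): 20 + 3 × 8 = 44 mg, against 4 × 10 = 40 mg scheduled (+10%). If the premedication already overrides the schedule, the starting total is 20 + 3 × 10 = 50 mg and the step is -12%.

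**Results that do not depend on the count.**

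1. At age 70 or over the schedule puts 10 mg on daratumumab days (cycle 1 days 1 and 8; day 1 from cycle 7, where the 10 mg weekly dose applies). The Table 6-4 note and Section 6.2.1.2 require 20 mg on the same days.
2. In cycles 1-2 the premedication alone, 4 × 20 = 80 mg, equals the whole scheduled total at age 70 or over. No step can go below it.
3. A patient for whom Table 6-5 orders permanent discontinuation still falls under Section 6.2.1.2, which requires dexamethasone before every injection.

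**The case against.** A reader might infer that one level down is no reduction for every patient from cycle 7 and doubles the dose for those aged 70 or over. The documents do not support that as a settled result, for four reasons.

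- It depends on reading level -1 as the fixed 20 mg rung. Table 6-5 speaks of decreases and decrements, and a move from 10 to 20 mg is neither. Counting from the current dose is at least as natural, and then nothing doubles.
- The two halves cannot both hold for patients aged 70 or over from cycle 7. The first also fails for patients under 70 already at level -1 before cycle 7, whose next level is 12 mg in non-daratumumab weeks.
- The 10 mg starting point is clear only in cycles 7-8. Section 6.2.4 limits the age rule to induction and gives 20 mg from cycle 9 without an age limit, yet the same rule lists 10 mg for cycle 7 onward.
- Section 6.3 calls the dexamethasone modifications guidelines that do not override clinical judgment, and Table 6-5 lists recommended actions.

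All four stand, and they remove any claim that the ladder fails for older patients at all times. They do not remove the undefined reference dose. By contrast, Section 6.3.3 anchors a pomalidomide reduction to the previous dose. Nor do they remove the premedication conflicts: the note to Table 6-4 is worded as mandatory, and guideline status does not tell a site which of two incompatible instructions to follow.

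**Conclusion.** The concern holds in a limited form. The reference dose for a level is undefined for patients scheduled at 20 or 10 mg. Depending on the count, the first step is 0% or -40% from 20 mg, and +100% or -20% from 10 mg, in non-daratumumab weeks. The increase under the fixed count is clear only in cycles 7-8.

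Three conflicts hold on either count: 20 mg against 10 mg on daratumumab days at age 70 or over, no possible reduction for those patients in cycles 1-2, and permanent discontinuation against premedication for all. The rise from 40 to 44 mg per cycle assumes counting from the current dose, a 10 mg schedule, and a 20 mg premedication applied only once the reduction starts; if it applied from the outset, the total falls from 50 to 44 mg.

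This is an inconsistency in safety instructions, softened by their guideline status. No effect on the primary endpoint is shown. Dexamethasone dose intensity (Section 3.3.5) is exploratory, and nothing there ties it to level labels.

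**What to change.** By amendment, state in Section 6.3.5 which dose a level is counted from. Then reconcile Table 6-4 and its note, Table 6-5, the pre-injection list in Section 6.2.1.2, and the age and cycle schedules in Sections 4.1 and 6.2.4. The result should give one consistent instruction for each scheduled dose by age and cycle, including age 70 or over from cycle 9, and for daratumumab days in a patient told to stop dexamethasone. The sponsor sets all doses and steps; none is proposed here. The same amendment can correct the pointer in Section 6.3, which sends the reader to Section 6.3.4 (clarithromycin) for dexamethasone. The cost is protocol wording only, with no added patients, visits or procedures.

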**Table 6-5 Dexamethasone Dose Adjustments for Adverse Events**

Adverse Event	Recommended Action
Dyspepsia, gastric or duodenal ulcer, gastritis Grade 1–2 (requiring medical management)	Treat with H2 blockers, sucralfate, or pantoprazole. If symptoms persist despite above measures, decrease dexamethasone dose by 1 dose level.
> Grade 3 (requiring hospitalization or surgery)	Hold dexamethasone until symptoms controlled. Restart at 1 dose decrement along with concurrent therapy with pantoprazole. If symptoms persist despite above measures, discontinue dex permanently.
Acute pancreatitis	Discontinue dexamethasone permanently.
Edema > Grade 3 (limiting function and unresponsive to therapy or anasarca)	Diuretics as needed, and restart dexamethasone at 1 dose decrement; if edema persists despite above measures, decrease dose another level. Discontinue dexamethasone permanently if symptoms persist despite second reduction.
Confusion or mood alteration > Grade 2 (interfering with function +/- interfering with activities of daily living)	Hold dexamethasone until symptoms resolve. Restart dexamethasone at 1 dose decrement. If symptoms persist despite above measures, reduce by another dose decrement.
Muscle weakness > Grade 2 (symptomatic and interfering with function +/- interfering with activities of daily living)	Decrease dexamethasone by 1 dose level. If weakness persists, decrease dose by 1 more dose level. Discontinue dexamethasone permanently if symptoms persist.
Hyperglycemia $\geq$ Grade 3	Treatment with insulin or other hypoglycemic agents as needed. If uncontrolled despite above measures, decrease dose by 1 dose level until levels are satisfactory.
Other nonhematologic Toxicity $\geq$ Grade 3 felt related to dexamethasone	Hold dexamethasone dose. Resume at 1 dose decrement when toxicity has resolved to Grade 2 or less or to baseline. If toxicity recurs, discontinue dexamethasone permanently.

#### **6.4 Excluded Concomitant Medications and Procedures**

The following medications and procedures are prohibited during the study.

Systemic treatment with concurrent drugs known to prolong the QT interval (see Appendix 12.3)

Systemic treatment with any of the following metabolizing enzyme inducers should be avoided, unless there is no appropriate alternative medication for the patient's use:

- Strong CYP3A inducers: rifampin, rifapentine, rifabutin, carbamazepine, phenytoin, and phenobarbital. For a more comprehensive list of CYP3A inducers, please refer to Appendix 12.4.

The following medicinal products and procedures are prohibited during the study.

- Excluded foods and dietary supplements include St. John's wort and Ginkgo biloba.
- Any antineoplastic treatment with activity against MM, other than study drugs
- Radiation therapy (note that, in general, the requirement for local radiation therapy indicates disease progression)
- Platelet transfusions to help patients meet eligibility criteria are not allowed within 3 days prior to study drug dosing for any dosing day

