### SCHEDULE OF STUDY PROCEDURES

Screening Phase  Day-28 to 0		Treatment	End of Treatm	Post-Treatment Observation Phase
		(Cycle is 28 days) +/- 3 days for Cycle 1 and 2, +/- 7 days for Cycles 3-30	At 1 year (+/- 7 days) & 90 days after last dose of study drug (+/-7 days)	Each cycle is 90 days, +/- 30 days for 24 months or until progression
Informed consent a	X			
Inclusion/exclusion criteria review	X			
Demography/Medical history	X			
Physical Exam	X	X b (every cycle)	X	
Vital signs c	X	X d (every cycle)	X	
Weight	X	X (every cycle)	X	
ECOG status	X	X (every cycle)	X	
ECG	X			
Echocardiogram	X		X	
Pulmonary function testing e	X e		X e	
Chest x-ray f				
NYHA classification	X	X (cycle 1 only)	X	
Patient Diary g	X	X (every cycle)	X	
Concomitant medications	Continuous from time of ICF until 30 days of last treatment			
Adverse events	Continuous from time of ICF until 30 days of last treatment			
Study Drug Administration				
Daratumumab 1800 mg SC dosing h		Daratumumab 1800 mg SC on Days 1, 8, 15, and 22 of Cycles 1 and 2 (weekly dosing), on Days 1 and 15 of Cycles 3 to 6 (every 2 weeks dosing), and on Day 1 of Cycle 7 and subsequent cycles (every 4 weeks dosing)		

Clarithromycin		500 mg PO bid continuous days 1-28 of cycles 1-8 only		
Pomalidomide		Pomalidomide 4 mg PO days 1-21		

Dexamethasone		Dexamethasone (Cycle 1 D1 & 8): 20 mg IV Cycle 1 D2 & D9: 20mg PO Cycle 1 D15 & D22: 40mg PO Cycles 2- 6: 40 mg PO qwk Cycles 7- 8: 20mg PO qwk Cycle 9+: 20mg PO qwk		
Prophylactic Medications				
Varicella Zoster Prophylaxis		Valacyclovir 500mg PO qd (or equivalent, renally dosed-adjusted)		
Gastrointestinal Prophylaxis		Pantoprazole 40 mg PO daily, or other		
Laboratory Assessments				
Pregnancy test i	X	X	X	
Blood typing/indirect antiglobulin test	X			
Hematology (CBC) with differential	X	On Days 1, 8, 15, and 22 for Cycles 1 and 2; On Days 1 and 15 for Cycles 3 through 6; D1 from Cycle 7 onward and as clinically indicated	X	
Serum chemistry j	X	On Days 1, 8, 15, and 22 for Cycle 1-2, Day 1, 15 for cycles 3-6 and day 1 of each subsequent cycle	X	
Hepatitis B and C screening k	X	HBV DNA monitoring q12weeks	X	X i
Disease Assessments				
Serum $\beta$ 2-microglobulin	X			
Serum free light chains	X	X (every cycle)	X	X (every cycle)

SPEP and IFE	X	X (every cycle)	X	X (every cycle)

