8. Females of childbearing potential (FCBP)† must have a negative serum or urine pregnancy test with a sensitivity of at least 25 mIU/mL within 10 – 14 days prior to and again within 24 hours of prescribing pomalidomide (prescriptions must be filled within 7 days) and must either commit to continued abstinence from heterosexual intercourse or begin TWO acceptable methods of birth control, one highly effective method and one additional effective method AT THE SAME TIME, at least 4 weeks before she starts taking pomalidomide FCBP must also agree to ongoing pregnancy testing. Men must agree to use a latex condom during sexual contact with females of child-bearing potential even if they have had a successful vasectomy. Females must agree not to donate eggs (ova, oocytes) and men not to donate sperm for the purpose of assisted reproduction during the study and for 4 weeks after the last dose of pomalidomide and for 3 months after the last dose of daratumumab. †A female of childbearing potential is a sexually mature woman who: 1) has not undergone a hysterectomy or bilateral oophorectomy; or 2) has not been naturally postmenopausal for at least 24 consecutive months (i.e., has had menses at any time in the preceding 24 consecutive months).
9. Able to take aspirin daily as prophylactic anticoagulation (patients intolerant to ASA may use warfarin or low molecular weight heparin).
10. Life expectancy  $\geq 3$  months
11. Subjects must meet the following laboratory parameters:

- i. Absolute neutrophil count (ANC)  $\geq 750$  cells/mm^3 ( $.75 \times 10^9/L$ )
- ii. Platelets count  $\geq 50,000/mm^3$  ( $50 \times 10^9/L$ )
- iii. Serum SGOT/AST  $\leq 2.0 \times$  upper limits of normal
- iv. Serum SGPT/ALT  $< 3.0 \times$  upper limits of normal (ULN)
- v. Serum CrCl  $\geq 30$  mL/min
- vi. Total bilirubin  $\leq 1.5 \times$  ULN (Total bilirubin  $\geq 1.5 \times$  ULN is acceptable if bilirubin is fractionated and direct bilirubin  $< 35\%$ ).
12. All study participants must be registered into the mandatory POMALYST REMS™ program and be willing and able to comply with the requirements of the POMALYST REMS™ program.

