### 6.2 Study Drug Administration

All protocol-specific criteria for administration of study drug must be met and documented before drug administration. Study drugs will be administered or dispensed only to eligible patients under the supervision of the investigator or identified sub-investigator(s). Patients should be monitored for toxicity, as necessary, and doses of daratumumab, pomalidomide, and dexamethasone should be modified or delayed as needed to accommodate patient tolerance to treatment (See Section 6.3).

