#### **6.3.1 Criteria for Beginning or Delaying a Subsequent Treatment Cycle**

Treatment with Daratumumab, Pomalidomide, and Dexamethasone will use a cycle length of 28 days. For a new cycle of treatment to begin, the patient must meet the following criteria:

- ANC must be  $\geq 1,000/\text{mm}^3$ .
- Platelet count must be  $\geq 75,000/\text{mm}^3$
- All other nonhematologic toxicity must have resolved to  $\leq$  Grade 2 or to the patient's baseline condition for cardiac toxicities (See Table 6.4 for definition of cardiac toxicities).

If the patient fails to meet the above-cited criteria for initiation of the next cycle of treatment, dosing should be delayed for 1 week. At the end of that time, the patient should be re-evaluated to determine whether the criteria have been met. If the patient continues to fail to meet the above-cited criteria, delay therapy and continue to reevaluate. The maximum delay before treatment should be discontinued will be 4 weeks or at the discretion of the Principal Investigator.

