### 6.3.2 Daratumumab Dose Modifications and Delays

No daratumumab dose modification (increase or decrease) is permitted.

During each cycle, the daratumumab dose must be held if any of the following criteria are met, to allow for recovery from toxicity.

- Grade 4 hematologic toxicity, or Grade 3 or higher thrombocytopenia with bleeding;
- Grade 3 or higher non-hematologic toxicities with the following exceptions:
  - Grade 3 nausea or Grade 3 vomiting that responds to antiemetic treatment,
  - Grade 3 diarrhea that responds to antidiarrheal treatment,
  - isolated Grade 3  $\gamma$ -glutamyltransferase elevation, or
  - Grade 3 fatigue or asthenia that was present at baseline or that lasts for <7 days after the last administration of daratumumab.

Daratumumab treatment should be resumed when the toxicity has resolved to  $\leq$  Grade 2. If the daratumumab administration does not commence within the prespecified window of the scheduled administration date as per Table 6-1, then the dose will be considered a missed dose. Administration may resume at the next planned dosing date.

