## **7. STUDY PROCEDURES**

### **7.1 Screening**

The screening (Pre-cycle) period occurs within 28 days prior to Cycle 1, Day 1 of therapy. Please see Schedule of Study Procedures for additional details.

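### Minor: the 3-day platelet-transfusion ban in Section 6.4 runs back from dosing, not from the qualifying sample, so a transfusion-supported count can satisfy inclusion 11.ii

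*Combined protocol and SAP*

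**What the plan says.** - **Section 5.1, inclusion 11.** Under "Subjects must meet the following laboratory parameters", item ii asks for a platelet count of at least 50,000/mm3. It attaches no condition about recent transfusion, and neither do the exclusion criteria or the schedule of procedures.
- **Section 7.1.** "The screening (Pre-cycle) period occurs within 28 days prior to Cycle 1, Day 1 of therapy". Section 4.1 and the schedule give the same 28-day window.
- **Section 6.4.** "Platelet transfusions to help patients meet eligibility criteria are not allowed within 3 days prior to study drug dosing for any dosing day". This is the only transfusion interval in the document.
- **Section 6.5.** Red cells and platelets may be given when clinically indicated.
- **Section 6.2.** Every criterion for giving study drug must be satisfied and recorded before it is given, and only eligible patients may be dosed.
- **Schedule of procedures.** After screening, blood counts are due "On Days 1, 8, 15, and 22 for Cycles 1 and 2".
- **Section 6.3.1.** "For a new cycle of treatment to begin, the patient must meet the following criteria", among them platelets of at least 75,000/mm3. The section heading refers to a subsequent cycle.
- **Section 6.3.2.** Daratumumab is held for "Grade 4 hematologic toxicity, or Grade 3 or higher thrombocytopenia with bleeding".
- **Table 6-3.** Pomalidomide is held below 50,000/mm3. Its first onset column is headed "Onset Day 2-14 of Cycle", and for later onset it refers to 6.3.1 for starting the next cycle.

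**The concern.** The stated purpose of the 6.4 rule and the event it is timed from do not match. The rule concerns transfusions used to meet eligibility, but eligibility on platelets is decided by a sample that may be drawn up to four weeks before the first dose. A ban covering the last 3 days before dosing says nothing about a transfusion shortly before an earlier sample.

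What is at stake is a patient whose unsupported count is below 50,000/mm3, the level at which Table 6-3 holds pomalidomide. That patient could be enrolled as eligible and possibly receive a first dose. Two features give this some clinical weight:

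- Inclusion 9 requires that the patient can take daily aspirin, or warfarin or low molecular weight heparin if intolerant. Section 6.2.4.1.2 gives aspirin 162 mg daily with pomalidomide.
- The backbone lowers platelets. Section 1.1 reports Grade 3/4 thrombocytopenia of 33% (Grade 4 16%) with clarithromycin, pomalidomide and dexamethasone. Section 1.3.2.2 reports 19% with daratumumab, pomalidomide and dexamethasone.

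**Working it through.** The plan gives no figure on this point, so the check is of timing and wording.

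**Set-up.** Put the first dose at time 0. Let the qualifying sample be drawn k days before dosing, with k from 0 to 28, which gives 29 permitted sample days. Let a platelet transfusion be given t days before dosing. It can support the sample only if it precedes it (t > k, or earlier on the same day).

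**What 6.4 bars.** A transfusion is barred only if both conditions hold: t is at most 3, and it was given to help meet eligibility criteria.

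**Guaranteed transfusion-free time before the sample.**

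| Reason for transfusion | Barred days before a sample at k | k = 0 | k = 1 | k = 2 | k = 3 to 28 |
|---|---|---|---|---|---|
| To meet eligibility (6.4) | max(0, 3 - k) | 3 | 2 | 1 | 0 |
| Clinically indicated (6.5) | 0 | 0 | 0 | 0 | 0 |

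A guarantee must hold whatever the reason for the transfusion, so it is the smaller entry in each column: 0 days on all 29 sample days.

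**Example.** Transfused on day -10 (t = 10) and sampled on day -9 (k = 9). The transfusion is 10 - 9 = 1 day before the sample. Because 10 > 3, Section 6.4 does not bar it even if it was given purely to qualify. If the count reads at least 50,000/mm3, 11.ii is met.

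**Does a later step re-test 11.ii?**

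1. Section 6.2 requires eligibility and documented dosing criteria. A supported count formally meets 11.ii, and 6.2 does not call for a fresh count.
2. The Cycle 1 Day 1 blood count shows the current value, but the schedule attaches no platelet limit to it.
3. Section 6.3.1 has a limit of 75,000/mm3. Applied at Cycle 1, it would turn away patients at 50,000 to 74,999/mm3 whom 11.ii admits. Its heading points to later cycles, and it carries no transfusion condition of its own.
4. Section 6.3.2 does not hold daratumumab for Grade 3 thrombocytopenia without bleeding.
5. The Table 6-3 onset columns begin at Day 2. Section 6.3 describes the pomalidomide modifications as guidance that does not override clinical judgement.

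**Under the amended wording**, t - k must be at least 3 days for every k and every reason for transfusion.

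**Primary design.** The rule of 8 or more responders in 40 has exact one-sided alpha 0.0242 at 9% and power 0.818 at 25%, within the stated bounds. The platelet rule does not enter either figure.

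**The case against.** The best defence is that the dosing anchor is deliberate. Section 6.2 requires criteria to be met and documented before drug is given, 6.4 links eligibility to every dosing day, and a blood count is due on Cycle 1 Day 1. Read together, they suggest a check at dosing that a transfusion may not prop up. Table 6-3 also sends cycle starts to 6.3.1; if that section governs Cycle 1, its limit is stricter than 11.ii. Bleeding risk at first dose depends on the count that day, not on a screening value up to 28 days old.

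Much of this stands. A Day 1 check is plausible, and early counts would probably expose a low value quickly. But no sentence says that 11.ii is re-tested at Cycle 1, and use of 6.3.1 there conflicts with the 50,000/mm3 entry limit. If eligibility in 6.4 means only fitness to be dosed, then 11.ii has no transfusion rule at all. Even with a firm Day 1 check, enrolment on a supported count remains possible.

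It is also fair to object that the 3-day interval is borrowed: nothing in the documents shows that 3 days is long enough before a sample. It is simply the protocol's own figure.

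**Conclusion.** The gap is real but minor. Section 6.4 misses its own stated purpose because it is timed from dosing, and 11.ii does not make up for it. The conclusion rests on the wording alone, taking the qualifying sample as any screening sample within the 28-day window.

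Three further inferences are not supported:

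- **That samples in the last three days are protected.** A reader might infer that 6.4 guarantees 1 to 3 clear days there and so confine the gap to the other 29 - 3 = 26 sample days. That treats 6.4 as a ban on all transfusions. It bars only those given to reach eligibility, so no day is guaranteed, and the 26-of-29 count should not be used as a measure of size.
- **That patients with low counts will be dosed unchecked.** The Day 1 and weekly counts, 6.2 and the holds make early detection likely. The documents give no rate of platelet transfusion during screening, so frequency is unknown and no patient count can be stated.
- **That the primary result is at risk.** Sample size, error rates and the primary analysis are unaffected.

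**What to change.** At the next amendment, add one sentence to Section 6.4 and repeat it in inclusion 11.ii: no platelet transfusion, for any reason, may be given within 3 days before the blood sample used to meet 11.ii. Keep the existing dosing-day rule in 6.4. Clinically indicated transfusion under 6.5 remains allowed; if one is given, the count is repeated after the interval and the repeat value decides eligibility. The cost is the added wording and a few repeat counts or screen failures.
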